7.1.6 Determining Attribution to the Investigational Agents

An assessment of the relationship between the AE and the medical intervention. CTCAE does not define an AE as necessarily “*caused by a therapeutic intervention*”. After naming and grading the event, the clinical investigator must assign an attribution to the AE using the following attribution categories:

| Relationship | Attribution | Description |
|---|--------------------|--------------------------------------|
| Unrelated to investigational agent/intervention | Unrelated | The AE is clearly NOT related |
| | Unlikely | The AE is doubtfully related |
| Related to investigational agent/intervention | Possible | The AE may be related |
| | Probable | The AE is likely related |
| | Definite | The AE is clearly related |

7.2 Adverse Event Reporting Requirements

7.2.1 Reporting to the IRB

1. Unanticipated problems involving risks to subjects or others will be reported promptly to the IRB if they:

- unexpected;
- related or possibly related to participation in the research; and
- suggests that the research places subjects or others at a greater risk of harm than was previously known or recognized.

If the adverse event does not meet all three (3) criteria listed above, the event does not have to be promptly reported to the Indiana University IRB. However, it should be reported at the time of continuing review.

2. Prompt reporting of unanticipated problems to the IRB is defined as within 5 days from becoming aware of the event.

7.2.2 Reporting to Exelixis

7.2.2.1 SAEs

As soon as an investigator becomes aware of an AE that meets the definition of ‘serious,’ this should be documented to the extent that information is available.

- IUSCC shall notify Exelixis within twenty-four (24) hours of making such discovery by submitting a completed SAE report form and any other pertinent SAE information as indicated on the SAE reporting form;
- The SAE reporting form must be submitted to Exelixis even if it is not felt to be drug related;
- Pregnancy (for a subject or for the partner of a subject), although not itself an SAE, should also be reported on a pregnancy form and be followed up to determine outcome, including spontaneous or voluntary termination, details of birth, and the presence or absence of any birth defects or congenital abnormalities;
- SAEs that must be recorded on an SAE Reporting form include the following:
 - all SAEs that occur after informed consent and through 30 days after the decision to discontinue study treatment (or the date the subject is deemed to be a screen failure);
 - any SAEs assessed as related to study treatment or study procedures, even if the SAE occurs more than 30 days after the decision to discontinue study treatment;

CONFIDENTIAL

- although most hospitalizations necessitate reporting of an SAE, some hospitalizations do not require SAE reporting, as follows: elective or previously scheduled surgeries or procedures for pre-existing conditions that have not worsened after initiation of treatment (e.g., a previously scheduled ventral hernia repair); pre-specified study hospitalizations for observation; or events that result in hospital stays of fewer than 24 hours and that do not require admission (e.g., an emergency room visit for hematuria that results in a diagnosis of cystitis and discharge to home on oral antibiotics). SAEs must, however, be reported for any surgical or procedural complication resulting in prolongation of the hospitalization.

IUSCC will report to Exelixis all SAEs that are sent to the FDA at the time of submission to the FDA. Follow-up information will be provided to Exelixis as reasonably requested. Send SAE reports on the MedWatch Report Form to:

Exelixis Drug Safety
[contact]
Email: [contact]

7.2.2.2 Study Initiation

IUSCC will provide the following to Exelixis prior to initiation of Exelixis support (provision of product and/or funding):

- Final study protocol
- Fully executed IST Agreement
- Regulatory Response Documentation (IND or CTA documentation if applicable)
- IRB/IEC approval

7.2.2.3 Study Maintenance

Throughout the study, IUSCC will provide the following to Exelixis:

- At least one safety study status update per year, to include information on enrollment and study completion dates.
- *Immediate* notification of any amendments made due to safety reasons.

7.2.2.4 Study Closure

IUSCC will provide Exelixis a copy of the IND Annual Report. Upon study closure, IUSCC will certify that all safety reporting obligations were met.

CONFIDENTIAL

7.2.3 Reporting to the FDA

Per CFR 312.32 (c), the investigator-sponsor of the IND must notify the Food and Drug Administration (FDA) and all participating investigators in a written IND safety report of any adverse experience. There are two types of reports to the FDA: 7-day and 15-day reports.

7.2.3.1 15-Day IND Reports:

The investigator-sponsor of the IND must notify the Food and Drug Administration (FDA) and all participating investigators in a written IND safety report of any:

- **suspected adverse reaction that is both**
- **serious and**
- **unexpected**

Each written notification shall be made as soon as possible, and no later than **15 calendar** days after the investigator-sponsor's initial receipt of the information.

7.2.3.2 7-Day Reports:

The investigator-sponsor must notify FDA and all participating investigators in a written IND safety report of any adverse experience:

- **fatal or life-threatening experience that is both**
- **associated with use of the drug and**
- **unexpected**

The FDA will be notified as soon as possible but no later than **7 calendar** days after initial receipt of the information.

7.2.3.3 Report Content:

Each written notification may be submitted on FDA Form 3500A or in a narrative format and must bear prominent identification of its contents, i.e., "IND Safety Report". For purposes of this protocol, the **MedWatch Report Form (FDA 3500A mandatory reporting), along with FDA Form 1571, and a cover letter** submitted to the appropriate FDA division, will serve as the written IND safety report. Follow-up information to a safety report should be submitted as soon as the relevant information is available.

Submit:

- MedWatch Report Form (FDA 3500A)

CONFIDENTIAL

- FDA Form 1571
- Cover Letter

The IUSCC Protocol Development Coordinator should be contacted to assist with all FDA submissions and will be provided with a copy of all events that are reported to the FDA. All IND submissions will be maintained in a master file in the Clinical Trials Office of the IU Simon Cancer Center.

7.2.4 Reporting to Participating Sites

Exelixis will send IND safety reports from external studies that involve the study drug to the Multicenter Network Associate Administrator, or designee. The Multicenter Network Associate Administrator, or designee, will forward the safety reports to the sponsor-investigator, or designee, who will review these reports and determine if revisions are needed to the protocol or consent. IUSCC will forward these reports to participating sites every 2 weeks.

For IND safety reports originating from this study, IUSCC will distribute reports which are serious, unexpected and associated with the study intervention (possibly, probably or definitely related) to all participating sites in the form of an Expedited Safety Report (external safety/IND safety report) within 15 calendar days from determination that the suspected adverse reaction qualifies for reporting. Copies of these External Safety Reports will be kept on file in the IUSCC CTO. Upon receipt from IUSCC, site investigators, or designees, are responsible for submitting these safety reports to their respective IRBs, as per their IRB policies.

Exelixis reserves the right to upgrade the investigator assessment of an SAE based on sponsor-investigator reporting responsibilities.

7.3 Other Safety Considerations

7.3.1 Laboratory Data

All laboratory data required by this protocol and any other clinical investigations should be reviewed. Any abnormal value that leads to a change in subject management (e.g., dose reduction or delay or requirement for additional medication or monitoring) or that is considered to be of clinical significance by the investigator should be reported as an AE or SAE as appropriate.

7.3.2 Pregnancy

If a subject becomes pregnant during the study, she will be taken off study treatment and will be followed through the end of her pregnancy. The investigator must inform the PI of the

CONFIDENTIAL

pregnancy. Forms for reporting pregnancies will be provided to the study sites upon request. The outcome of a pregnancy (for a subject or for the partner of a subject) and the medical condition of any resultant offspring must be reported to Exelixis or designee. Any birth defect or congenital anomaly must be reported as an SAE, and any other untoward events occurring during the pregnancy must be reported as AEs or SAEs, as appropriate.

7.3.3 Medication Errors/Overdose

Any study drug administration error or overdose that results in an AE, even if it does not meet the definition of serious, requires reporting within 24 hours to Exelixis or designee.

7.3.4 Follow-Up of Adverse Events

Any related SAEs or any AEs assessed as related that led to treatment discontinuation, including clinically significant abnormal laboratory values that meet these criteria, ongoing 30 days after the decision to discontinue study treatment must be followed until either resolution of the event or determination by the investigator that the event has become stable or irreversible. This follow-up guidance also applies to related SAEs that occur *> 30 days after the decision to discontinue* study treatment. The status of all other continuing AEs will be documented as of 30 days after the decision to discontinue study treatment.

8 STATISTICAL CONSIDERATIONS

8.1 General Considerations

Statistical analysis of this study will be the responsibility of the Department of Biostatistics at Indiana University School of Medicine. Parameter estimates and relevant summary statistics will be reported for both efficacy and safety outcomes. Continuous variables will be summarized by means, medians, minima, maxima and standard deviations. Categorical variables will be summarized by frequencies and percentages. Missing data will not be imputed. Additional exploratory analysis will be conducted when appropriate. Changes from the analysis plan will not require an amendment to the protocol unless it changes a significant feature in the protocol. The statistical analysis methods are outline below.

8.2 Study Design

This is a single arm two-stage Phase II study. No randomization or blinding is involved.

8.3 Definition of Endpoints

Objective response (radiographic response) rate: proportion of all subjects with confirmed PR or CR according to RECIST 1.1, from the start of treatment until disease progression/recurrence

CONFIDENTIAL

(taking as reference for progressive disease the smallest measurements recorded since the start of treatment)

Disease control rate: proportion of all subjects with stable disease (SD) for 8 weeks, or partial response (PR), or complete response (CR) according to RECIST 1.1, from the start of treatment until disease progression/recurrence (taking as reference for progressive disease the smallest measurements recorded since the start of treatment).

Progression-free survival: a measurement from the date of first treatment until the criteria for disease progression is met as defined by RECIST 1.1 or death occurs. Subjects who have not progressed will be right-censored at the date of the last disease evaluation.

Overall survival (OS): a measurement from the date of first treatment until death from any cause.

Safety: Adverse event terms recorded in the eCRFs defined by the National Cancer Institute (NCI) CTCAE v4.03. Seriousness, severity grade and relationship to study treatment will be assessed by the investigator.

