| Contrast enhanced CT or MRI ⁶ | X | | | | | | X (every 8 weeks) | | |
| Archival Tissue Collection/Correlative Studies | | | | | | | | | |
| Blood sample collection ⁸ | | | X ¹⁰ | X | X | | X | | |
| Tissue sample collection ⁸ | X ⁷ | | | | | | | | |

CONFIDENTIAL

Footnotes:

1. Follow-up may be done by medical record review or phone call to subject and/or next of kin.
2. Subjects will be monitored for adverse events (AEs) from the time of first study intervention (i.e., biopsy, if needed, or treatment, whichever comes first).
3. Additional follow-up will occur for subjects with AEs related to study treatment that are ongoing at the time of this visit, and for subjects with SAEs related to study treatment that occur after the time of this visit.
4. A Full physical exam will be done in the pre-treatment period and on Cycle 1/Day 1. Physical exams may also be done by the investigator or qualified designee throughout participation in the trial as clinically indicated.
5. Vital signs include: height (at screening only), weight, temperature, pulse, respiratory rate, and blood pressure.
6. All sites of known disease must be assessed.
7. Patients will be asked for archival tissue during the screening period. Archival tissue is required pre-treatment as part of study eligibility to test for EGFR and c-MET expression. KRAS will also be tested if previous KRAS testing was not done or results are unknown AND there is adequate tissue available from tissue collected at screening
8. Only samples collected from eligible patients during the screening period will be utilized for the correlative studies which are outlined in this trial. Samples collected from ineligible patients during screening will be discarded.
9. Only for women of childbearing potential.
10. This sample may be collected any time after enrollment so long as it occurs before the patient takes his/her first dose of study medication on Cycle 1/Day 1.
11. The window for this test is within 28 days of starting treatment.

CONFIDENTIAL

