6.3 Treatment Period

During the Treatment Period subjects will receive cabozantinib and erlotinib until either disease progression, the occurrence of unacceptable drug-related toxicity or for other reason(s) for subject withdrawal as described in Section 3.6.

If the subject is unable to have a study assessment taken within the defined time window due to an event outside of his or her control (e.g., clinic closure, personal emergency, inclement weather, vacation), the assessment should be performed as close as possible to the required schedule.

Regular tumor assessments should be performed in accordance to the guidelines in Section 6.3.1.8 to determine if PD is present.

The Treatment Period ends when a subject receives his or her last dose of study treatment; the subject then enters the Post-Treatment Period.

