6.3.1.8 Disease Assessment

Contrast enhanced imaging studies (CT or MRI) will be performed at screening and every 8 weeks beginning Cycle 3/Day 1. All sites of known disease must be assessed. CT modalities should be done according to standard of care for the subject's disease.

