6.5 Survival Follow-Up

Subjects will be followed every 3 months for up to 2 years after treatment discontinuation for survival via medical record review or phone call to the subject and/or next of kin.

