8.9 Efficacy Analysis

An exact binomial test will be used to test the hypothesis that radiographic response (ORR) is greater than 15%). ORR and DCR will be estimated with 95% exact binomial confidence intervals. Median PFS and OS will be estimated using 95% confidence intervals based on the exponential distribution. Safety and tolerability data will be tabulated.

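### Tumor imaging ends with the last dose, so a patient who stops without progression has no later progression date. Median PFS is biased upward if that patient's death counts as the event.

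*Combined protocol and SAP*

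**What the plan says.** Section 8.3 defines PFS as "a measurement from the date of first treatment until the criteria for disease progression is met as defined by RECIST 1.1 or death occurs". It then adds: "Subjects who have not progressed will be right-censored at the date of the last disease evaluation". Section 8.9 gives the estimator: "Median PFS and OS will be estimated using 95% confidence intervals based on the exponential distribution".

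Imaging "will be performed at screening and every 8 weeks beginning Cycle 3/Day 1" (section 6.3.1.8). Section 6.3 ties this to the Treatment Period: "Regular tumor assessments should be performed in accordance to the guidelines in Section 6.3.1.8 to determine if PD is present". It closes that period regardless of disease status: "The Treatment Period ends when a subject receives his or her last dose of study treatment; the subject then enters the Post-Treatment Period". In the schedule of assessments (6.1) the CT/MRI row is blank for the post-treatment visit and for survival follow-up. The visit at 30 to 37 days (6.4.1.1) covers laboratory tests and physical examination, without a scan. After that, section 6.5 provides for contact every 3 months "for up to 2 years after treatment discontinuation for survival via medical record review or phone call".

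Section 3.6 lists several reasons to stop that need no RECIST progression: an adverse event, investigator judgment, noncompliance, need for another anticancer treatment, and loss of clinical benefit. No rule says how PFS is handled after such a stop, after new anticancer therapy, or after missed scans. The only other text on censoring, in 4.5.4 on palliative bone radiation, leaves the choice open.

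**The concern.** A patient who stops before RECIST progression leaves the imaging schedule at the last dose. Any later progression is not recorded by design, and the next dated outcome that the plan collects is death. If death is the PFS event, the recorded time equals or exceeds the time that continued scanning would have given.

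PFS is a secondary endpoint. It is also the outcome for the biomarker Cox models and is central to the correlative analysis in section 8.10. With a single arm, no control group shares the distortion. Because 8.3 does not settle these patients' status, two analysts could report different medians from the same data.

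**Working it through.** **The plan's own figures.** The documents give no target, assumed median or precision for PFS, so there is no PFS figure to reproduce. The response design in 8.5 does reproduce. The early termination probability is 0.975^11 = 0.757, and the expected sample size is 11 + (1 − 0.757) × 26 = 17.32. The exact two-stage calculation gives error rates of 0.045 and 0.198. None of this depends on PFS.

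**One patient (hypothetical).** Scans fall every 56 days, or 56/30.4375 = 1.84 months. Suppose a patient stops at month 2.5 for toxicity, progresses at month 3 and dies at month 7.
- Scans continued: progression is seen at the second scan, 2 × 1.84 = 3.68 months (event).
- Death counted as the event: 7 months (event).
- Second sentence of 8.3 applied literally: 1.84 months (censored).

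**Estimator.** The exponential median is ln 2 × (total time) / (number of events). Time added between an unseen progression and death goes straight into the numerator.

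**Size.** These inputs are assumptions, not taken from the documents: median time to progression 2-3.5 months, median survival after progression 3-4 months, and stops uniform between 0.5 and 3 months. Of all patients, 10%, 20% or 30% are destined to stop, which makes about 8%, 16% or 24% stop before progression. Simulation compares the plan with scanning continued to progression or death:

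| Destined to stop | Death is the event, all treated | Death is the event, only patients with an on-treatment scan |
|---|---|---|
| 10% | +4% to +9% | about +2% to +3% |
| 20% | +8% to +17% | about +3% to +6% |
| 30% | +12% to +26% | about +5% to +10% |

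The last column matters because section 8.4.3 limits efficacy analysis to patients evaluated for the primary endpoint. The first on-treatment scan is at 1.84 months, so (1.84 − 0.5)/2.5 = 54% of the assumed stopping window comes before it.

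If the same patients are censored at the last scan and stopping is unrelated to progression, the change is between 0 and −1%.

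**Wider grid.** A second simulation used median time to progression of 2-4 months, median post-progression survival of 2-4 months, and 10-30% actually stopping without documented progression, in all treated patients. Stopping was either unrelated to progression or placed in the scan interval where progression would have been found.
- Death as the event: +2% to +35%, upward in all 36 scenarios. With medians of 3 and 4 months and 20% stopping for unrelated reasons, 3.61 months becomes 4.14 (4.14/3.61 = 1.15).
- Censoring at the last scan: 0% to −2% when stopping is unrelated, and +6% to +32% when it anticipates progression.

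**The case against.** A reader might infer that median PFS is biased upward whichever way 8.3 is applied. The documents do not support that. Read literally, the second PFS sentence censors these patients, and censoring distorts the estimate upward only if stopping is linked to coming progression. That link is plausible, since loss of clinical benefit is a stopping reason in 3.6, but it is an assumption.

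A reader might also take the all-treated figures as the size. Section 8.4.3 can be read to remove patients who stop before the first scan, which cuts the rise to less than half. It does not define being evaluated, so both ranges must be shown. Such an exclusion could bring selection of its own, which is a separate matter.

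Three further points narrow the issue. Section 4.3.1 lets a patient continue on one drug, and an interruption does not by itself end treatment, so those patients stay on the scan schedule. An off-treatment scan that meets RECIST 1.1 already falls within the definition in 8.3 if someone obtains it. The share who stop without progression is unknown.

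Finally, PFS is only estimated and drives no decision. With 37 events, an exact exponential 95% interval runs from about −26% to +42% around the estimate, wider than most of these shifts. That limits the weight of the point. It does not remove it, because the interval does not allow for a systematic shift and the remedy is cheap.

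**Conclusion.** The gap stands: no progression date is collected after the last dose, and 8.3 does not say what happens to a patient who then dies without documented progression. If the death is the event, the exponential median PFS is biased upward, by about 4-26% in all treated patients or about 2-10% among those with an on-treatment scan. If the patient is censored at the last scan, the bias is about zero or upward, depending on whether stopping anticipates progression. All sizes rest on assumed progression, survival and stopping rates. PFS and the biomarker models in 8.10 are affected. The primary response test, the stopping rule and the sample size of 37 are not. This should be corrected, but it does not threaten the trial's main conclusion.

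**What to change.** 1. **Section 6.5.** At the existing 3-monthly record review, also collect the date of progression on standard-of-care imaging and the start date of any new anticancer therapy.
2. **Section 8.3.** Reconcile the two PFS sentences so that death without documented progression has one stated status. State that off-treatment imaging meeting RECIST 1.1 counts as progression.
3. **Section 8.9.** Add a sensitivity analysis that censors at the last scan when death follows two or more missed scan intervals (16 weeks). Progression known only from clinic notes does not meet the RECIST definition in 8.3, so it belongs in a sensitivity analysis only.

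The cost is two form fields and a little extra analysis. No protocol scans or patients are added. The downside is that off-study imaging is less uniform in timing and technique than protocol scans. Where follow-up is by phone alone, imaging records may have to be requested.
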